6.2. Exclusion Criteria

Subjects will be excluded from study enrollment if they meet any of the following criteria at screening and/or enrollment:

- [8] are investigative site personnel directly affiliated with this study or their immediate families. Immediate family is defined as a spouse, biological or legal guardian, child, or sibling.
- [9] are Lilly employees or employees of third-party organizations involved with the study
- [10] are currently enrolled in a clinical trial involving an investigational product or any other type of medical research judged not to be scientifically or medically compatible with this study

- [11] have participated, within the last 30 days, in a clinical trial involving an investigational product. If the previous investigational product has a long half-life, 3 months or 5 half-lives (whichever is longer) should have passed.
- [12] have previously completed or withdrawn from this study or any other study investigating LY2951742, and have previously received LY2951742
- [13] have known allergies to LY2951742, related compounds, or any components of the formulation, or history of significant atopy
- [14] have received treatment with any monoclonal antibody targeting the CGRP pathway (including LY2951742), or have received other biologic agents (such as monoclonal antibodies) within 4 months or 5 half-lives (whichever is longer) prior to dosing
- [15] have a history of multiple (3 or more) or severe allergies or has had an anaphylactic reaction to prescription or non-prescription drugs or food
- [16] have allergies to either humanized monoclonal antibodies, diphenhydramine, epinephrine, or methylprednisolone
- [17] have an abnormality in the 12-lead ECG that, in the opinion of the investigator, increases the risks associated with participating in the study
- [18] have a clinically significant abnormality in vital signs as determined by the investigator
- [19] have a history or presence of cardiovascular, respiratory, hepatic, renal, gastrointestinal, endocrine, hematological, or neurological disorders capable of significantly altering the absorption, metabolism, or elimination of drugs; of constituting a risk when taking the investigational product; or of interfering with the interpretation of data (appendectomy and cholecystectomy are allowed)
- [20] have known or ongoing clinically significant neuropsychiatric disorders. Neuropsychiatric disorders that required active treatment (pharmacological or nonpharmacological) should be considered clinically significant.
- [21] regularly use known drugs of abuse and/or show positive findings on urinary drug screening
- [22] show evidence of human immunodeficiency virus (HIV) infection and/or positive human HIV antibodies
- [23] show evidence of hepatitis C and/or positive hepatitis C antibody
- [24] show evidence of hepatitis B and/or positive hepatitis B surface antigen
- [25] are women who are lactating

- [26] intend to use over-the-counter or prescription medication within 7 days prior to dosing and during the study (especially systemic glucocorticoids, immunomodulatory drugs, drugs with propensity for dermal reactions, drugs with known hepatic toxicity, etc). Stable doses of HRT (including estrogen, estrogen/progesterone combination, and thyroid replacement therapy) are allowed for inclusion. Occasional acetaminophen up to a 2-g dose in a 24-hour period, stool softener, or nasal saline preparations may be allowed for inclusion at the discretion of the investigator.
- [27] have donated blood of more than 500 mL or have undergone major surgery within the last month
- [28] are unwilling to refrain from consuming xanthine-containing food and drink from 24 hours prior to admission to the CRU, or unwilling to abide by caffeine restrictions as specified in Section 6.3.1
- [29] have an average weekly alcohol intake that exceeds 21 units per week (males) and 14 units per week (females), or are unwilling to stop alcohol consumption 48 hours prior to admission to CRU and during residence in the CRU, and for 48 hours prior to each outpatient visit, or are unwilling to restrict alcohol intake to no more than 21 units per week (males) and 14 units per week (females), with no more than 3 units consumed per day, at all other times during the outpatient period (1 unit = 12 oz or 360 mL of beer; 5 oz or 150 mL of wine; 1.5 oz or 45 mL of distilled spirits)
- [30] currently smoke in excess of 5 cigarettes/day or use tobacco or nicotine substitutes (within the last 6 months of screening), or are unwilling to abide by CRU smoking restrictions
- [31] have had lymphoma, leukemia, or any malignancy within the past 5 years except for basal cell or squamous epithelial carcinomas of the skin that have been resected with no evidence of metastatic disease for 3 years
- [32] have any other condition which, in the opinion of the investigator and/or Lilly, precludes the subject from providing informed consent, following the protocol procedures and restrictions, or completing the protocol

6.3. Lifestyle and/or Dietary Requirements

Throughout the study, subjects may undergo medical assessments and review of compliance with requirements before continuing in the study.

6.3.1. Xanthines/Caffeine, Alcohol, and Tobacco

Subjects will not be allowed xanthine consumption for 24 hours prior to admission to the CRU. While resident in the CRU, subjects should abide by the CRU caffeine intake guidelines.

Alcohol consumption is not allowed from 48 hours prior to all study visits. While resident in the CRU, subjects should abide by the CRU guidelines. During the outpatient period, alcohol consumption is limited to no more than 21 units per week (males) and 14 units per week

(females), with no more than 3 units to be consumed per day, except for the 48 hours prior to each outpatient visit, during which alcohol consumption is not permitted.

While resident in the CRU, subjects should abide by the CRU guidelines for smoking. Subjects will be questioned about their smoking habits at screening.

6.3.2. Activity

Subjects should avoid strenuous physical activity 48 hours prior to CRU admission until at least 30 days after dosing.

6.3.3. Blood or Plasma Donation

Blood or plasma donations are not permitted for 150 days after dosing.

6.4. Screen Failures

Individuals who do not meet the criteria for participation in this study (screen failure) will not be re-screened.

7. Treatment

7.1. Treatment Administered

This study involves a comparison of the PK of LY2951742 solution formulation administered as a manual PFS versus an investigational autoinjector. [Table CGAQ.2](#) shows the treatment regimens.

Table CGAQ.2. Treatments Administered

Treatment name	LY2951742	LY2951742
Total dose:	240 mg	240 mg
Concentration:	120 mg/mL	120 mg/mL
No. of injections:	2 × 1 mL	2 × 1 mL
Formulation and presentation:	Solution in a prefilled syringe	Solution in an autoinjector

The investigator or designee is responsible for:

- explaining the correct use of the investigational products to the site personnel
- verifying that instructions are followed properly
- maintaining accurate records of investigational product dispensing and collection
- returning all unused medication and autoinjectors to Lilly or its designee at the end of the study
- reporting product quality issues/complaints within the specified time
- and returning any autoinjectors that do not operate correctly to Lilly for further evaluation. A product complaint form must be filed with each device returned.

Note: In some cases, sites may destroy the material if, during the investigative site selection, the evaluator has verified and documented that the site has appropriate facilities and written procedures to dispose of clinical trial materials.

7.1.1. Packaging and Labeling

LY2951742 as a PFS will be supplied as an injectable solution in a 1-mL, single-dose, disposable manual syringe. Each syringe of LY2951742 will be designed to deliver 120 mg of LY2951742. A dose will consist of two 1-mL PFS, with each syringe containing 120 mg of LY2951742, for a total dose of 240 mg LY2951742.

LY2951742 as an investigational autoinjector will be supplied as an injectable solution in a 1-mL, single-dose, disposable autoinjector. Each autoinjector of LY2951742 will be designed to deliver 120 mg of LY2951742. A dose will consist of two 1-mL autoinjectors, with each autoinjector containing 120 mg of LY2951742, for a total dose of 240 mg LY2951742.

Clinical trial materials will be labeled according to the country's regulatory requirements. Autoinjectors will be labeled as "investigational device".

7.1.2. Drug Delivery Devices

A PFS and an investigational autoinjector containing 1 mL of 120 mg/mL LY2951742 solution will be provided for use in the study.

7.2. Method of Treatment Assignment

Subjects will be randomized in a 1:1 ratio to treatment with LY2951742 administered as a PFS or autoinjector. Assignment to the injection device (PFS or autoinjector) and injection site (arm, abdomen, or thigh) will be determined by a computer-generated randomization schedule provided to each site.

7.2.1. Selection and Timing of Doses

Subjects will be allocated to fixed-dose (240 mg LY2951742) treatment according to the randomization schedule.

The actual time of dose administration will be recorded in the subject's electronic case report form (eCRF).

7.3. Blinding

This will be an open-label study.

7.4. Dose Modification

This section is not applicable for this study.

7.5. Preparation/Handling/Storage/Accountability

Only participants enrolled in the study may receive investigational product and only authorized site staff may supply or administer study treatment. All study treatments should be stored in an environmentally controlled and monitored (manual or automated) area in accordance with the labeled storage conditions with access limited to the investigator and authorized site staff. The syringes of LY2951742 for injection (PFS and autoinjector) should be stored in the refrigerator (2 to 8°C). The syringes should be removed from the refrigerated storage and allowed to equilibrate to room temperature for approximately 30 minutes before administration.

The investigator or designee is responsible for study treatment accountability, reconciliation, and record maintenance (such as receipt, reconciliation, and final disposition records).

7.6. Treatment Compliance

The investigational products will be administered at the clinical site, and documentation of treatment administration will occur at the site.

7.7. Concomitant Therapy

Stable doses of HRT, including estrogen, estrogen/progesterone combination, and thyroid replacement therapy, will be allowed during the study. Over-the-counter medications or other prescription medications are to be avoided within 7 days prior to dosing and during the study (especially systemic glucocorticoids, immunomodulatory drugs, drugs with propensity for dermal reactions, drugs with known hepatic toxicity, etc).

If the need for concomitant medication arises, inclusion or continuation of the subject may be at the discretion of the investigator after consultation with a Lilly Clinical Pharmacologist (CP) or Clinical Research Physician (CRP). Occasional acetaminophen, up to a 2-g dose in a 24-hour period, stool softener, or nasal saline preparations may be used at the discretion of the investigator. Any additional medication used during the course of the study must be documented.

7.8. Treatment after the End of the Study

This section is not applicable for this study.

8. Discontinuation Criteria

8.1. Discontinuation from Study Treatment

Not applicable for this single-dose study.

8.1.1. *Discontinuation of Inadvertently Enrolled Subjects*

If the sponsor or investigator identifies a subject who did not meet enrollment criteria and was inadvertently enrolled, a discussion must occur between the Lilly CP or CRP and the investigator to determine if the subject may continue in the study. If both agree it is medically appropriate to continue, the investigator must obtain documented approval from the Lilly CP or CRP to allow the inadvertently enrolled subject to continue in the study.

8.2. Discontinuation from the Study

Subjects will be discontinued in the following circumstances:

- Enrollment in any other clinical trial involving an investigational product or enrollment in any other type of medical research judged not to be scientifically or medically compatible with this study
- Participation in the study needs to be stopped for medical, safety, regulatory, or other reasons consistent with applicable laws, regulations, and good clinical practice (GCP)
- Investigator Decision
 - the investigator decides that the subject should be discontinued from the study
- Subject Decision
 - the subject requests to be withdrawn from the study

Subjects who discontinue the study early will have end-of-study procedures performed as shown in the Schedule of Activities (Section 2).

8.3. Subjects Lost to Follow-Up

A subject will be considered lost to follow-up if he or she repeatedly fails to return for scheduled visits and is unable to be contacted by the study site. Site personnel are expected to make diligent attempts to contact subjects who fail to return for a scheduled visit or were otherwise unable to be followed up by the site.

9. Study Assessments and Procedures

Section 2 lists the Schedule of Activities, detailing the study procedures and their timing (including tolerance limits for timing).

Appendix 2 lists the clinical laboratory tests that will be performed for this study.

Appendix 5 provides a summary of the maximum number and volume of invasive samples, for all sampling, during the study.

Unless otherwise stated in subsections below, all samples collected for specified laboratory tests will be destroyed within 60 days of receipt of confirmed test results. Certain samples may be retained for a longer period, if necessary, to comply with applicable laws, regulations, or laboratory certification standards.

Investigators must document their review of each laboratory safety report.

9.1. Efficacy Assessments

This section is not applicable for this study.

9.2. Adverse Events

Investigators are responsible for monitoring the safety of subjects who have entered this study and for alerting Lilly or its designee to any event that seems unusual, even if this event may be considered an unanticipated benefit to the subject.

The investigator is responsible for the appropriate medical care of subjects during the study.

The investigator remains responsible for following, through an appropriate health care option, AEs that are serious or otherwise medically important, considered related to the investigational product or the study, or that caused the subject to discontinue the investigational product before completing the study. The subject should be followed until the event resolves, stabilizes with appropriate diagnostic evaluation, or is reasonably explained. The frequency of follow-up evaluations of the AE is left to the discretion of the investigator.

After the informed consent form (ICF) is signed, study site personnel will record, via eCRF, the occurrence and nature of each subject's pre-existing conditions. Additionally, site personnel will record any change in the condition(s) and the occurrence and nature of any AEs.

The investigator will interpret and document whether or not an AE has a reasonable possibility of being related to study treatment, study device, a study procedure, concomitant treatment or pathologies.

A "reasonable possibility" means that there is a cause and effect relationship between the investigational product, study device, and/or study procedure and the AE.

Planned surgeries should not be reported as AEs unless the underlying medical condition has worsened during the course of the study.

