9.2.1. Serious Adverse Events

An SAE is any AE from this study that results in one of the following:

- death
- initial or prolonged inpatient hospitalization
- a life-threatening experience (that is, immediate risk of dying)
- persistent or significant disability/incapacity
- congenital anomaly/birth defect
- events considered significant by the investigator based upon appropriate medical judgment
- when a condition related to the autoinjector necessitates medical or surgical intervention to preclude either permanent impairment of a body function or permanent damage to a body structure, the serious outcome of “required intervention” will be assigned.

Study site personnel must alert Lilly, or its designee, of any SAE within 24 hours of investigator awareness of the event via a sponsor-approved method. If alerts are issued via telephone, they are to be immediately followed with official notification on study-specific SAE forms. This 24-hour notification requirement refers to the initial SAE information and all follow-up SAE information.

Investigators are not obligated to actively seek AEs or SAEs in subjects once they have discontinued from and/or completed the study (the subject summary eCRF has been completed). However, if the investigator learns of any SAE, including a death, at any time after a subject has been discharged from the study, and he/she considers the event reasonably possibly related to the study treatment or study participation, the investigator must promptly notify Lilly.

Pregnancy (maternal or paternal exposure to investigational product) does not meet the definition of an AE. However, to fulfill regulatory requirements any pregnancy should be reported following the SAE process to collect data on the outcome for both mother and fetus.

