9.2.1.1. Suspected Unexpected Serious Adverse Reactions

Suspected unexpected serious adverse reactions (SUSARs) are serious events that are not listed in the IB and that the investigator identifies as related to investigational product or procedure. United States 21 Code of Federal Regulations (CFR) 312.32 and European Union Clinical Trial Directive 2001/20/EC and the associated detailed guidances or national regulatory requirements in participating countries require the reporting of SUSARs. Lilly has procedures that will be followed for the recording and expedited reporting of SUSARs that are consistent with global regulations and the associated detailed guidances.

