### **9.5 Safety and Tolerability Assessments**

#### **9.5.1 Adverse events**

Where changes in severity are recorded in the Case Report Form (CRF), each separate severity of the adverse event (AE) will be reported in the listings, only the most severe will be used in the summary tables. A pre-existing condition is defined as an AE that starts before the subject has provided written informed consent and is ongoing at consent. A non-treatment emergent AE is defined as an AE which starts after informed consent but prior to dosing. A treatment-emergent AE is defined as an AE which occurs postdose or which is present prior to dosing and becomes more severe postdose.

All AEs will be listed. Treatment-emergent AEs will be summarized by treatment, severity and relationship to the study drug. The frequency (the number of AEs, the number of subjects experiencing an AE and the percentage of subjects experiencing an AE) of treatment-emergent AEs will be summarized by treatment, Medical Dictionary for Regulatory Activities (MedDRA) version 19.1 system organ class and preferred term. The summary and frequency AE tables will be presented for all causalities and those considered related to the study drug. Any serious AEs will be tabulated.

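### Protocol 9.2 defines a reasonable possibility of relatedness as an existing cause and effect relationship, which is stricter than the term itself and could under-classify suspected reactions

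*Protocol*

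**What the plan says.** Protocol 9.2 sets the causality question: "The investigator will interpret and document whether or not an AE has a reasonable possibility of being related to study treatment". The same sentence extends the question to the study device, study procedures, concomitant treatment and other pathologies. The answer is yes or no. Next comes the only definition of the threshold in either document: a reasonable possibility "means that there is a cause and effect relationship between the investigational product, study device, and/or study procedure and the AE".

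Other places use relatedness without defining it again:

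- Protocol 9.2.1 requires prompt notification of an SAE learned of after discharge if "he/she considers the event reasonably possibly related to the study treatment or study participation".
- Protocol 9.2.1.1 describes SUSARs as "serious events that are not listed in the IB and that the investigator identifies as related to investigational product or procedure".
- Protocol 10.3.1.1 presents TEAEs by the investigator's view of association and reports the number of product-related SAEs.
- SAP 9.5.1 states: "The summary and frequency AE tables will be presented for all causalities and those considered related to the study drug".

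**The concern.** The definition and the term disagree. A reasonable possibility is a threshold of suspicion. A statement that a causal relationship exists is a threshold of affirmation, and the defining sentence contains nothing like may, suggest or possible to soften it. An investigator who suspects a reaction but cannot say that the drug, device or procedure caused it would answer yes under the term and no under the definition.

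The design makes that situation likely. Each subject receives one dose, so there is no rechallenge. Both arms receive the same drug at the same dose, so there is no untreated comparator. Protocol 3.3 asks investigators to watch for unexpected, off-target and idiosyncratic effects because relatively few people have been exposed, and such effects usually first appear as suspicions. The study is also multi-center. If some sites follow the term and others the definition, the related-event counts will mix two standards.

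**Working it through.** There is no figure to reproduce: the point concerns the wording of a definition and involves no sample size, power or variance. The check sets the definition beside each provision that uses relatedness, or might be thought to.

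| Provision | Where | Depends on the relatedness call? |
|---|---|---|
| Incidence of TEAEs by association; number of product-related SAEs | Protocol 10.3.1.1 | Yes |
| Related-only summary and frequency tables | SAP 9.5.1 | Yes |
| Investigator's duty to follow an AE to resolution | Protocol 9.2 | Only for AEs that are not serious, not otherwise medically important and did not lead to discontinuation |
| SUSAR definition | Protocol 9.2.1.1 | Yes; it names only the investigator's judgement |
| Notification of SAEs learned of after discharge | Protocol 9.2.1 | Yes, through its own phrase, which is close to the defined term |
| Notification of SAEs during the study | Protocol 9.2.1 | No: "Study site personnel must alert Lilly, or its designee, of any SAE within 24 hours of investigator awareness of the event" |
| Sponsor review of SAEs | Protocol 9.4.5 | No; not limited to related events |
| Listing of all AEs, all-causality tables, serious-AE table | SAP 9.5.1 | No |
| TEAE, the secondary safety endpoint | Protocol 4 and Appendix 1 | No; defined without regard to causality |
| Primary pharmacokinetic comparison | Protocol 10.3.2.2, SAP 9.3.2 | No |

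Three things follow.

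1. The definition is the outlier. The causality question, the post-discharge rule and the word suspected in SUSAR all express possibility. Only the defining sentence expresses existence.

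2. During the study, a strict reading changes the label on an event, not whether it is recorded. An event classed as unrelated still appears in the listings and the all-causality tables. If it is serious, it still reaches the sponsor.

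3. The post-discharge case has the least protection. Sites need not actively seek events after a subject has left, and the duty to notify covers only SAEs that the investigator considers reasonably possibly related. If the investigator reads that phrase through the definition in 9.2, the sponsor need not be told and has nothing to review. This matters most for early withdrawals: Protocol 3.2 gives a half-life of 25 to 30 days, so a subject who leaves in the first weeks still carries drug.

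How many events could change class cannot be calculated. Neither document gives a rate of possibly related events or says how investigators apply the sentence.

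**The case against.** A reader might infer that plausible events will in fact be recorded as unrelated and lost from the related tables and from SUSAR reporting, or that the protocol demands proof. The documents do not support either reading. Proof is not mentioned, and no section directs investigators to class uncertain events as unrelated. The question they answer is still framed as a reasonable possibility. The defining sentence can also be read as saying which kind of relationship counts, causal and not merely temporal. Appendix 1 draws that distinction in its definition of an AE. Site training and eCRF instructions, which are not among the documents, may settle the matter.

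The safeguards are also substantial. Every SAE during the study goes to the sponsor whatever its cause. The sponsor reviews SAEs and consults an independent safety physician when appropriate. Investigators must report any event that seems unusual. On expedited reporting, Protocol 9.2.1.1 adds: "Lilly has procedures that will be followed for the recording and expedited reporting of SUSARs that are consistent with global regulations". The post-discharge rule states its own threshold and does not refer back to the definition. No inferential safety analysis is planned (SAP 9.5.9), and both arms work under the same definition.

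Most of this stands, and it limits the point to a risk under literal or uneven application. Two things remain. The benign reading has to be supplied by the reader, because the sentence as written says that a relationship exists. And the in-study safeguards do not extend to an SAE that an investigator learns of after discharge and decides not to report.

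**Conclusion.** The concern holds as an inconsistency in a stated rule. The definition in Protocol 9.2 is stricter than the term it defines and than the post-discharge wording in Protocol 9.2.1. Followed literally, or by some sites only, it could under-classify suspected events in the five places in the table that depend on relatedness. Loss of in-study SUSARs is possible but not established, given the 24-hour rule and the sponsor's procedures.

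The size cannot be stated from the documents. The effect is confined to the related subsets and the duties tied to them. It does not reach the secondary safety endpoint, the full AE and SAE reporting, or the primary comparison of devices. The conclusion assumes that at least some investigators would let the definition override the question, and that the eCRF guidance does not already correct it.

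**What to change.** Reword the defining sentence in Protocol 9.2 so that a reasonable possibility means there is reason to suspect, from facts or arguments pointing that way, that the product, the device or a study procedure caused the event. This brings it into line with the post-discharge threshold in 9.2.1 and with the idea of a suspected reaction in 9.2.1.1. Put the same wording in the eCRF completion instructions so that all sites apply one standard. The SAP needs no change, because its tables use whatever classification is recorded.

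The cost is one sentence in the protocol and one in the eCRF guide. The small downside is that somewhat more events will be classed as related.
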